4.3 Healing Confirmation

Only those subjects whose study ulcer is 100% re-epithelialised without drainage as determined by the PI or designee during a TV, will be scheduled for a Healing Confirmation Visit (HCV). The HCV is to be scheduled a minimum of 7 days after the first determination of re-epithelialisation.

During the HCV perform the activities in the following order:

- Administer the CWIS and EQ-5D-5L questionnaires in the participant's primary language.

- Administer the study ulcer pain VAS assessment.
- Check for any changes in the participant's health and update the AE or SAE CRF pages if applicable.
- Assess concomitant medications.
- Assess compression bandaging (See Section 9.8).
- Assess study ulcer healing (to be performed by treating PI or designee).

If the study ulcer remains 100% re-epithelialised without drainage:

- Obtain a digital image of the study ulcer site.
- Provide appropriate follow-up therapy for the participant and the healed ulcer and exit the participant from the study.
- Complete the remaining applicable visit (TV5) procedures.

If the study ulcer remains 100% re-epithelialised without drainage at the HCV, the date of healing for the purpose of study results will be the date 100% re-epithelialisation without drainage was first determined by the PI or designee.

If the study ulcer is NOT 100% re-epithelialised without drainage:

- Complete the remaining visit (TV5) procedures.
- Check for signs of clinical infection.
- Clean the study ulcer.
- Obtain a digital image of the study ulcer.
- Provide appropriate follow-up therapy for the participant and the non-healed ulcer and exit the participant from the study.

4.4 Follow-up Phase

Participants who completed TV5 will be contacted after 4, 8 & 12 weeks to find out the status of the study wound.

At week 13, 17 and 21; a member of the research team (at the clinical site) will contact the patient to find out

- whether the wound is healed or not healed
- if healed (the date wound was healed)

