Comparator Product: Multilayer, multicomponent compression therapy intended for the treatment of VLU (Standard Care)	
Protocol Number: FSK-VLU- 004	Indication: Venous Leg Ulcers (VLUs)

conjunction with SC, to SC alone, in the treatment of patients with VLUs. There are two arms in the study consisting of: 1) Participants randomised to receiving SC only; 2) Participants randomised to receiving SC and geko™ 12 hours daily.
 
A non adherent (NA) wound contact dressing and/or an absorbent dressing may be used if required, at the Investigator's discretion in addition to SC. All dressing use and reason for dressing use will be recorded.
 
Multilayer, multicomponent compression therapy intended for the treatment of VLU based on local best practice will be used.
 
The study will be a multinational, multicentre study with study centres in the UK & Europe
 
The study will have a four-week Run-in Phase, a four-week Treatment Phase, 3 months Follow-up Phase and a Healing Confirmation visit (HCV) as applicable.
 
At or up to 21 days before RV1, written informed consent from the participant will be obtained by the Investigator or suitably qualified designee before the performance of any protocol-specific procedure.
	
<pre> graph LR Screening[Screening] --> Recruitment[Recruitment] Recruitment --> RunIn[Run-In Phase Standard of Care (0- 4 weeks)] RunIn --> Randomisation[Randomisation] Randomisation --> SC[Standard of Care (SC)] Randomisation --> SCplus[SC plus geko™ 12hr daily] SC --> Treatment1[Treatment Phase (4 - 8 weeks)] SCplus --> Treatment2[Treatment Phase (4 - 8 weeks)] Treatment1 --> FollowUp1[Follow-Up Phase Call at 1M, 2M and 3M post Treatment Phase] Treatment2 --> FollowUp2[Follow-Up Phase Call at 1M, 2M and 3M post Treatment Phase] </pre> 
Note: Patient is deemed to have completed the trial once their wound is healed or they have completed the run-in, treatment and follow-up phases.
	

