
Randomisation
 
This is a multi-centre randomised study. Participants will be allocated to treatment groups using Adaptive Covariate Randomisation using an on-line randomisation tool.
 
The randomisation will be applied centrally across the sites.
 
Blinding
 
The independent wound expert measuring the wound area and assessing the healing status of the wound will be blinded to the treatment assignments.
 
The Run-in Phase (RV1 to RV5) is designed to determine each participant's LHR when treated with SC alone. Participants will be seen and evaluated on a weekly basis.
 
The Treatment Phase (TV1 to TV5)
	

Name of Sponsor/Company: Firstkind Ltd, [name]	
Name of Study Product: geko™ neuromuscular stimulator	
Comparator Product: Multilayer, multicomponent compression therapy intended for the treatment of VLU (Standard Care)	
Protocol Number: FSK-VLU- 004	Indication: Venous Leg Ulcers (VLUs)

Participants will be seen and evaluated on a weekly basis. Efficacy evaluations each week will include Investigator assessment of wound healing and measurements of ulcer size using digital photos. Safety evaluations during the Treatment Phase will consist of adverse event assessments at each visit.
 
The Follow-up Phase (FP1-FP3)
 
Participants will be contacted at week 13, week 17 & week 21 to find out when their wound is healed.
	

Healing Confirmation Visit (HCV)
 
Participants whose ulcer presented with 100% re-epithelialisation without drainage as determined by the PI or designee will be scheduled for a Healing Confirmation Visit (HCV) in a minimum of 7 days time after which they will exit the study whether or not healing is confirmed.
 
Duration of Treatment: The duration of the Treatment Phase is four weeks.
 
Total Study Duration: The total study duration is a maximum of nine weeks: four weeks Run-in Phase and four weeks Treatment Phase followed by a HCV in a minimum of 7 days time if applicable. Participants who completed TV5 will have further 12 week Follow-up phase.
	

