2.1.3 Participant Reported Secondary Efficacy Endpoints

The participant reported secondary efficacy endpoints are:

Time from TV1 to clinically significant pain reduction measured using a Visual Analogue Scale (VAS) instrument. For the purpose of this protocol a clinically significant reduction of pain is a mean reduction of ≥ 20.65 mm or a mean decrease of $\geq 10\text{-}20\%$ in pain as measured on a 0-100 mm VAS (23; 24).

Time from TV1 to first instance of no study ulcer pain measured using VAS.

(No pain = < 5 mm on VAS when VAS scores: 0-4 mm = no pain; 5-44 mm = mild pain; 45-74 mm = moderate pain; and 75-100 mm = severe pain) (1).

Pain score at EOT measured using VAS

Change from TV1 in Quality of Life (QoL) at EOT, assessed using the Cardiff Wound Impact Schedule (CWIS)

Change from TV1 in QoL at EOT, assessed using EQ-5D-5L

Wound closure as reported by participants during the Follow-up Phase (FP1-FP3)

The two QoL instruments, the CWIS a wound specific QoL instrument, and the EQ-5D-5L, a standardised instrument for measuring generic health status, will be provided to the participants for completion at RV1, TV1 and at EOT. In case of withdrawal all attempts should be made to obtain final QOL assessments.

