During the Run-in Phase participants will be evaluated on a weekly basis. Efficacy evaluations each week will include Investigator assessment of wound healing and measurements of ulcer size using digital images. For the purpose of this study, healing is defined as 100% re-epithelialisation without drainage confirmed at the Healing Confirmation visit (HCV). The compression bandaging system of choice based on local best practice in the study centre in question will be used.

The results of the four-week Run-in Phase during which only SC will be used as treatment, will provide an SC only healing trajectory (LHR curve) (22) for each of the participants and each participant will serve as his/her own control.

At RV1, the Investigator will assess and confirm the patient's eligibility and select the study ulcer. Each participant will have only one VLU selected as the study ulcer. In the situation where a participant has more than one VLU at the RV1 visit, the Investigator will select the largest VLU that meets the eligibility criteria of the protocol as the study ulcer. If other ulcerations are present on the same leg they should be more than 2 cm apart from the study ulcer.

At the first Treatment Phase visit (TV1), once the Investigator has confirmed the participant's continued eligibility, randomisation and assignment to study treatment will take place.

The total maximum study duration is nine weeks, followed up by twelve weeks Follow-up Phase. All participants remaining in the study at the final Treatment Phase visit, TV5, will complete study visits unless they present with 100% re-epithelialisation without drainage as determined by the PI or designee, in which case they will be scheduled for a Healing Confirmation Visit (HCV) in a minimum of 7 days. All participants attending a HCV will complete study visits at this visit regardless if healing is confirmed or not.

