4.2.4 Final Treatment Phase Visit (TV5)

Perform the assessments/activities in the following order:

- Administer the CWIS and EQ-5D-5L questionnaires in the participant's primary language
- Administer the study ulcer pain VAS assessment.
- Assess and sign the participant diary card (gekoTM groups only).
- Check for any changes in the participant's health and update the AE or SAE CRF pages if applicable.
- Assess concomitant medications.
- Assess compression bandaging (See Section 9.8).
- Assess study ulcer healing (to be performed by treating PI or designee)

If the study ulcer is 100% re-epithelialised without drainage:

- Obtain a digital image of the study ulcer site.
- Provide appropriate follow-up therapy for the healed ulcer and schedule the participant for a Healing Confirmation Visit (HCV) in a minimum of 7 days.
- Administer the CWIS and EQ-5D-5L questionnaires in the participant's primary language.
- Complete the remaining applicable visit procedures.

If the study ulcer is NOT 100% re-epithelialised without drainage:

- Complete the remaining visit procedures.
- Check for signs of clinical infection.
- Clean the study ulcer.
- Digital image of the study ulcer (if debridement is planned this will be the pre-debridement image). N.B., all study ulcer measurements will be performed using the pre-debridement images.
- Debride the study ulcer to obtain a clean, granulating ulcer base with minimal adherent slough, at the discretion of the Investigator.
- If applicable, obtain a digital image of the study ulcer (post-debridement).
- Provide appropriate follow-up therapy for the non-healed ulcer and exit the participant from the study.

Table 2: Schedule of Events – Treatment Phase

Activity/Assessment	TV1 (pre-rand)	TV1 (post-rand)	TV2	TV3	TV4	TV5 /Final Visit
CWIS and EQ-5D-5L assessments	✓					✓
Study ulcer pain assessment (VAS)	✓		✓	✓	✓	✓
Assess for AEs	✓		✓	✓	✓	✓
Assess concomitant medications	✓		✓	✓	✓	✓
Assess compression bandaging	✓		✓	✓	✓	✓
Study ulcer exudate assessment	✓		✓	✓	✓	✓
Venous Clinical Severity Score						✓
Leg oedema assessment	✓		✓	✓	✓	✓
Study ulcer healing assessment			✓ [∞]	✓ [∞]	✓ [∞]	✓ [∞]
Study ulcer cleaning	✓		✓	✓	✓	✓
Study ulcer margin assessment	✓		✓	✓	✓	✓
Study ulcer surrounding skin assessment	✓		✓	✓	✓	✓
Study ulcer bed appearance	✓		✓	✓	✓	✓
Signs of infection of study ulcer	✓ [¶]		✓ [¶]	✓ [¶]	✓ [¶]	✓ [¶]
Study ulcer image(s)	✓ [⌘]		✓ [⌘]	✓ [⌘]	✓ [⌘]	✓ [⌘]
Study ulcer debridement	✓ [§]		✓ [§]	✓ [§]	✓ [§]	✓ [§]

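### Follow-up wound closure is sought only from participants who completed TV5, while anyone who closes earlier exits at the healing confirmation visit, so a comparison among those followed can shrink or hide a benefit

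*Combined protocol and SAP*

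**What the plan says.** Section 2.1.3 and the synopsis list as a participant-reported secondary endpoint "Wound closure as reported by participants during the Follow-up Phase (FP1-FP3)".

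On who is followed, Section 4.4 says "Participants who completed TV5 will be contacted after 4, 8 & 12 weeks to find out the status of the study wound", and the synopsis (Total Study Duration) agrees: "Participants who completed TV5 will have further 12 week Follow-up phase".

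On who leaves, the synopsis says that participants found closed attend an HCV, "after which they will exit the study whether or not healing is confirmed". Section 3 (Study Design) has the same rule: "All participants attending a HCV will complete study visits at this visit regardless if healing is confirmed or not". Section 4.3 instructs exit in both its healed and its not-healed branch. Section 4.2.4, for an ulcer still open at TV5, says "Provide appropriate follow-up therapy for the non-healed ulcer and exit the participant from the study".

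On analysis, Section 10.10.1 makes the ITT population primary for secondary endpoints. Section 10.7.3 omits follow-up closure from its list. Section 10.12.1 gives it no test, denominator or rule for early healers. Section 10.11 defines treatment failure for the Treatment Phase only.

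**The concern.** Entry to follow-up depends on what happened to the ulcer after randomisation. If the device speeds healing, more geko participants than control participants will close at TV2 to TV4, attend the HCV and leave before any call is due. Those who remain are, by selection, the slower healers, and more have been removed from the geko arm. A comparison among them is no longer a comparison of the randomised groups and tends to understate a real benefit.

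Participants whose HCV does not confirm healing are a separate problem. They leave with an open ulcer and nobody asks about it again.

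The exit instruction in Section 4.2.4 adds a practical risk. It applies to the unhealed TV5 completers whom Section 4.4 requires sites to call, so a site cannot follow both literally.

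**Working it through.** **The plan's own figure.** None exists for this endpoint. The only current calculation (Section 10.5.2) is for the paired healing-rate comparison: difference 0.58, SD 0.97 mm/week, 80% power, two-sided 0.05, stated n = 25. The normal formula gives (0.97 × (1.960 + 0.842) / 0.58)² = 21.95, so 22. The exact noncentral-t calculation gives 24 (power 0.801; 0.818 at n = 25). The stated figure is reproduced to within one participant, but it has no bearing on follow-up closure.

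**Who reaches the calls, as written**

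| Course | Called under 4.4? | Closure status by week 21 |
|---|---|---|
| Closed at TV2–TV4, confirmed at HCV | No | Known from recorded healing date (4.3) |
| Closed at TV2–TV4, not confirmed at HCV | No | Lost |
| First closed at TV5 | Yes under 4.4; exits at HCV under 4.3 | Contradictory |
| Open at TV5 | Yes under 4.4; exits under 4.2.4 | Contradictory |
| Withdrawn in Treatment Phase, TV5 assessments done (5.2) | Not stated | Unclear |

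**Size of the selection.** Let C be closure by week 21 in all randomised participants and e the share that closes early and exits. The formula assumes that every early exit is a true closure.

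- Closure among those followed = (C − e) / (1 − e).
- Closure with all randomised as denominator and early healers not counted = C − e.

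C and e are assumptions. I take C = 60% on standard care (SC) and 70% on geko, a true difference of 10 points, and 30 per arm, since the protocol gives 60 in total and no ratio.

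| e, SC vs geko | Among those followed | Difference | All randomised, early healers uncounted | Difference | Expected followed |
|---|---|---|---|---|---|
| 5% vs 10% | 55/95 = 57.9% vs 60/90 = 66.7% | +8.8 | 55% vs 60% | +5 | 28.5 vs 27 |
| 10% vs 20% | 50/90 = 55.6% vs 50/80 = 62.5% | +6.9 | 50% vs 50% | 0 | 27 vs 24 |
| 20% vs 40% | 40/80 = 50% vs 30/60 = 50% | 0 | 40% vs 30% | −10 | 24 vs 18 |

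**A second set of assumptions.** Suppose that closure after TV5 among those still open is 35% in both arms. Early exit of 5% vs 15% gives cumulative closure of 0.05 + 0.95 × 0.35 = 38.3% vs 0.15 + 0.85 × 0.35 = 44.8%, a gain of 6.5 points. Early exit of 10% vs 40% gives 41.5% vs 61.0%, a gain of 19.5 points. Among those followed, the difference is 0 in both cases.

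**Power after correction.** At 30 per arm and two-sided 0.05, a comparison of cumulative closure has about 7% power for 38.3% vs 44.8% and about 32% for 41.5% vs 61.0% (normal approximation; about 24% with Fisher's exact test in the latter case).

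**The case against.** The strongest reply is that the protocol never prescribes an analysis restricted to TV5 completers. Section 10.10.1 makes ITT primary for secondary endpoints, and detail is left to a separate SAP. Confirmed early healers are not lost: under Section 4.3 "the date of healing for the purpose of study results will be the date 100% re-epithelialisation without drainage was first determined", and the synopsis says "Patient is deemed to have completed the trial once their wound is healed or they have completed the run-in, treatment and follow-up phases". Cumulative closure could be derived for them from planned data.

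This stands as far as it goes. It makes confirmed early healing a gap in definition, not a loss of data. It does not remove the problem. ITT fixes who is in the denominator, but nothing says that an early healer counts as closed on an endpoint worded as closure reported during FP1–FP3. With that denominator and early healers uncounted, the distortion is larger, as the table shows.

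A reader might infer three stronger things that the documents do not support.

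- **That withdrawals are excluded from the calls.** Section 5.2 has TV5 assessments performed at withdrawal and does not say whether that counts as completing TV5. This is ambiguity.
- **That a real benefit will vanish.** Among those followed, it reaches zero only in the most extreme of the three 60%/70% scenarios. That scenario needs 40% of the geko arm to close and exit before TV5, so by TV4, three weeks after randomisation. If the 40% includes ulcers first closed at TV5, it overstates the share removed, because those participants did complete TV5.
- **That the trial's main conclusions are at risk.** Primary linear healing rate and incidence of healing at EOT retain early healers.

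The exit wording in Section 4.2.4 may be left over from before the Follow-up Phase was added by amendment (Appendix 7). It still needs correcting.

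**Conclusion.** The concern holds for one secondary endpoint. The contact rule and the exit rules together select the followed group on a post-randomisation outcome, and no other section repairs this. Under assumed closure of 60% vs 70%, a true difference of 10 points becomes 8.8, 6.9 or 0 among those followed, depending on how many close early. If early healers stay in the denominator uncounted, it becomes +5, 0 or −10. The direction follows from the design if the device speeds healing. The size is illustrative, because the protocol gives no rates for this endpoint.

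Information is truly lost for participants whose HCV does not confirm healing, and possibly for withdrawals. For confirmed early healers it can be recovered if the rule is written before analysis. The amendment is worth making but is not critical to the trial's primary conclusion.

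**What to change.** 1. Define the endpoint as cumulative closure from TV1 to week 21 in all randomised participants. Count HCV-confirmed healing as closed from the date it was first determined. State that the endpoint is first closure, so that later re-opening does not change it.
2. Make the FP1–FP3 calls to every randomised participant without confirmed healing who has not withdrawn consent. This includes those who leave after an unconfirmed HCV and those who stop treatment early.
3. Reconcile the exit wording in the synopsis and Sections 3, 4.2.4 and 4.3 with Section 4.4, and cover participants first closed at TV5. State in Section 5.2 whether assessments at withdrawal count as completing TV5.
4. Add the endpoint to Sections 10.7.3 and 10.12.1 with its denominator, Fisher's exact test (already planned for incidence of healing) and a stated rule for participants not reached.
5. Report clinician-confirmed and self-reported closure separately as well as combined.

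The cost is a short amendment and a few extra telephone calls by site staff, with no extra visits. Two drawbacks remain: the endpoint mixes clinician-confirmed and self-reported closure, and power at about 30 per arm stays low. The change removes a bias; it does not make the endpoint decisive.

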4.5 Unscheduled Visits

Unscheduled visits may be required in addition to the visits detailed above. Additional visits are at the discretion of the Investigator. An example of an unscheduled visit is when a change of compression bandaging is required between scheduled visits. The details of these unscheduled visits with participants will be recorded in the medical records/source documents and on the CRF.

4.6 Missed Visits

If a participant misses a visit, the site is to make every effort to have the participant return as soon as possible to make up the visit. Once the participant is seen, he/she is to return to his/her original weekly visit schedule. For example, if a participant was seen regularly on Mondays but missed a scheduled Monday visit and came in on Wednesday, he/she should return the next Monday to maintain his/her weekly Monday visit schedule

5 Participant Completion and Withdrawal

5.1 Participant Completion

A participant whose study ulcer has healed will be considered as having completed the study. For the purpose of this study healing is defined as 100% re-epithelialisation with no drainage as determined by the PI or designee. The 100% re-epithelialisation and absence of drainage must be confirmed at a subsequent clinic visit (HCV) in a minimum of 7 days (See Section 4.3). If 100% re-epithelialisation of the study ulcer with no drainage is confirmed at the HCV, the date of healing will be the date the ulcer was first determined by the PI or designee as 100% re-epithelialised and without drainage.

5.2 Premature Withdrawal / Discontinuation from the Study

A participant who is randomised and has completed TV1 of the Treatment Phase but who does not complete the study, as defined in Section 5.1, has prematurely discontinued.

All participants have the right to withdraw at any point during the study without prejudice to his/her treatment. It will be documented whether or not a participant completed the clinical study. If for any participant, study treatment or observations were discontinued, the reason(s) will be recorded.

The Investigator can discontinue a participant at any time if it is considered medically necessary.

In addition, participants will be withdrawn from the study, at the Investigator's discretion, if any of the following occur:

A participant is significantly non-compliant with the requirements of the protocol.

A participant has revascularisation surgery on the leg with the study ulcer.

The study ulcer cannot be compressed.

The study ulcer merges with an adjacent ulcer.

The reason for treatment discontinuation or withdrawal from the study will be recorded in the source documents and on the appropriate page of the CRF. Every attempt should be made to complete the relevant CRF pages.

Before a participant is identified as lost-to-follow up, the site should make all reasonable efforts to contact the participant. These attempts must be documented and should include at a minimum one phone call and one letter/email.

Participants who meet the criteria for premature withdrawal during the Treatment Phase will have TV5 assessments performed.

In the event that a participant is prematurely discontinued from the study at any time due to an AE or SAE, the procedures stated in Section 5.2 must be followed.

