Indication for Use: Indicated for use as an adjunct to Standard Care (SC) in the treatment of Venous Leg Ulcers (VLUs)	
Objective: The objective of this study is to compare the efficacy of a daily geko™ device treatment duration of 12 hours, in conjunction with SC, to SC alone, in patients with venous leg ulcers.	
Endpoints: Primary Efficacy The primary efficacy endpoint is linear healing rate (LHR) of the study ulcer from first Treatment Phase visit (TV1) to the End of Treatment (EOT) as compared with LHR from first Run-in Phase visit (RV1) to TV1. 
• EOT is defined as Treatment Phase visit 5 (TV5), withdrawal or that Treatment Phase visit at which 100% re-epithelialisation without drainage is first determined by the Principal Investigator (PI) or designee, whichever comes first. Each participant will be used as his/her own control. Wound area will be measured by a blinded independent wound expert using digital images taken at RV1, TV1 and at EOT. “Healing” of the study ulcer is determined by the PI or designee. “Healing” is defined as 100% re-epithelialised without drainage as confirmed at the Healing Confirmation visit (HCV).	

Name of Sponsor/Company: Firstkind Ltd, [name]	
Name of Study Product: geko™ neuromuscular stimulator	
Comparator Product: Multilayer, multicomponent compression therapy intended for the treatment of VLU (Standard Care)	
Protocol Number: FSK-VLU- 004	Indication: Venous Leg Ulcers (VLUs)

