2.1 Efficacy Endpoints

2.1.1 Primary Efficacy Endpoint

The primary efficacy endpoint is linear healing rate (LHR) from TV1 to EOT as compared with LHR from RV1 to TV1. LHR will be calculated by linear regression of the 4 measurements in each phase, with linear wound edge advance being based on the change with respect to time of wound area divided by perimeter, according to Vidal's method (22) [Each participant will be used as his/her own control, i.e. a participant's healing trajectory before introduction of treatment will be compared to his/her healing trajectory after introduction of treatment. Wound area and perimeter will be measured by a blinded independent wound expert using digital images taken at baseline (RV1), first treatment visit (TV1) and at EOT.

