2.1.2 Secondary Efficacy Endpoints

The secondary efficacy endpoints are:

- Weekly LHR measured by an independent blinded wound expert using digital images taken at each weekly visit until TV5, withdrawal or healing whichever comes sooner.
- Wound healing status at baseline and EOT assessed by an independent blinded wound expert using PWAT to evaluate digital images taken at RV1, TV1 and at withdrawal, healing or at the end of the Treatment Phase (TV5), whichever comes sooner.
- Incidence of healing at EOT, as determined by the Investigator

“Healing” of the study ulcer is determined by the PI or designee. “Healing” is defined as 100% re-epithelialised without drainage as confirmed at the Healing Confirmation visit (HCV).

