6.3 Participant Investigational Device Use

Each geko™ device can be used only twice. Participants randomised to the geko™ 12 hour daily treatment groups will at each visit be provided with a sufficient number of geko™ devices to last until the next scheduled Treatment Phase visit. Participants should ensure that they always have enough devices to carry them through to the next scheduled Treatment Phase visit. Participants randomised to either geko™ group will be provided with a diary card on which their geko™ usage will be recorded. The participants should bring the diary card with them at each site visit at which the cards will be verified and signed.

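### Sections 5.2 and 13.4 let staff remove a randomised participant from the study for non-compliance, which cuts short the ITT primary LHR and loses later images; any shift in the mean is small

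*Combined protocol and SAP*

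**What the plan says.** Section 5.2 states that "participants will be withdrawn from the study, at the Investigator's discretion, if any of the following occur". The first reason listed is "A participant is significantly non-compliant with the requirements of the protocol", with no threshold. Under section 13.4 the sponsor decides whether a participant with a deviation continues, and may discontinue that participant. Neither provision is automatic.

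Withdrawal fixes the end of the outcome window. The Synopsis says: "EOT is defined as Treatment Phase visit 5 (TV5), withdrawal or that Treatment Phase visit at which 100% re-epithelialisation without drainage is first determined", whichever comes first. Section 2.1.1 runs the primary LHR from TV1 to EOT and adds: "LHR will be calculated by linear regression of the 4 measurements in each phase". Section 2.1.2 takes "images taken at each weekly visit until TV5, withdrawal or healing whichever comes sooner". Section 10.10.1 makes ITT the primary population, and section 10.4 blinds only the wound expert.

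Some data are kept at exit. Section 5.2 says: "Participants who meet the criteria for premature withdrawal during the Treatment Phase will have TV5 assessments performed". It gives no date, but the EOT definition points to the day of withdrawal. Under section 4.4, "Participants who completed TV5 will be contacted after 4, 8 & 12 weeks to find out the status of the study wound", so the calls are probably lost to anyone withdrawn earlier.

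**The concern.** Compliance is observed after randomisation and can depend on the allocated treatment. Both arms must attend visits and wear compression. The geko arm must also use the device daily and keep a diary; section 6.3 says: "The participants should bring the diary card with them at each site visit at which the cards will be verified and signed". Site staff therefore see device compliance in one arm only, and removal for non-compliance may be more frequent there. The documents give no rate by arm.

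For a removed participant, the treatment-phase slope describes healing up to exit, not healing over four weeks as allocated, and it rests on fewer images. If healing would have slowed after device use stopped, the later and slower weeks are missing from the slope. PWAT, VAS and quality of life are also read at EOT and so are taken earlier. A later SAP can set rules for missing values but cannot recover images that were never taken.

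**Working it through.** **1. The plan's own figure.** Section 10.5.2 gives a mean within-arm change of 0.58 mm/week, SD 0.97, 80% power, two-sided 0.05, n = 25. The normal approximation is ((1.960 + 0.842) × 0.97 / 0.58)² = 21.95, so 22. The exact paired t gives 24 (power 0.801), and n = 25 gives power 0.818. The stated 25 is reproduced to within one participant. At n = 25 the SE of the arm mean is 0.97/√25 = 0.194.

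**2. Does the text end the outcome window?**

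| Step | Source |
|---|---|
| Removal is from the study, not only from treatment | 5.2; 13.4 similar |
| Withdrawal is an EOT event | Synopsis, Endpoints |
| Primary LHR runs to EOT, in ITT | 2.1.1, 10.10.1 |
| Weekly images stop at withdrawal | 2.1.2 |
| A section keeping a participant judged significantly non-compliant under observation to TV5 | none found |

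**3. Size of any shift in the geko mean.** Assumptions:
- The full 0.58 mm/week accrues only during device use. This is a ceiling, because 0.58 is a change from run-in and not an effect against SC.
- Use stops after week 1, 2 or 3.
- Exit follows 0, 1 or 2 visits later.
- Between 0 and 20% of the arm is affected. Section 10.2 puts all discontinuation at 20% at most.

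The shift per affected participant is the least-squares slope to exit minus the slope over all planned points.

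Example with five points (TV1–TV5), stop after week 1, exit at TV3:
- Slope to exit on 0, 0.58, 0.58 = (0.58 − 0)/2 = 0.290.
- Full slope on 0, 0.58, 0.58, 0.58, 0.58 = 0.58 × (−1 + 0 + 1 + 2)/10 = 0.116.
- Difference = 0.174.

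Differences in mm/week per affected participant, for stopping after week 1, 2, 3:

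| Points used | Immediate exit | One-visit lag | Two-visit lag |
|---|---|---|---|
| TV1–TV5 (five) | 0.464, 0.290, 0.116 | 0.174, 0.116, 0 | 0.058, 0, 0 |
| TV1–TV4 (four) | 0.406, 0.174, 0 | 0.116, 0, 0 | 0, 0, 0 |
| TV2–TV5 (four) | no slope, 0.406, 0.174 | 0, 0.116, 0 | 0, 0, 0 |

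Both four-point readings are shown because section 2.1.1 speaks of four measurements while TV1–TV5 is five visits.

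Shift in the arm mean = share affected × difference:
- One-visit lag, 20%: 0.20 × 0.174 = 0.035 (five points); 0.20 × 0.116 = 0.023 (four points).
- One-visit lag, 5%: 0.009 and 0.006.
- Two-visit lag, 20%: 0.20 × 0.058 = 0.012 (five points); 0 (four points).
- Immediate exit, 20%: 0.20 × 0.464 = 0.093 (five points); 0.20 × 0.406 = 0.081 (four points).
- Device never used, no device effect, or the same healing rate after exit: 0.

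The one-visit-lag maximum of 0.035 is 0.0348/0.58 = 6% of the assumed change and 0.0348/0.194 = 0.18 SE.

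**4. What an amendment can still correct.** Section 3.1.1 randomises 60; 30 per arm is assumed because no ratio is stated. Section 10.5 planned the interim at about 60% enrolled. If 60% of the arm has finished treatment (an assumption), 12 of 30 remain. At 20% affected that is 2.4 people, and the correctable shift is 0.035 × 12/30 = 0.014 mm/week (0.07 SE). At 5% it is 0.6 of a person and 0.009 × 12/30 = 0.003 (0.02 SE).

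**5. Precision lost.** The measurement-error variance of a slope is proportional to 1/Sxx.
- Five points: Sxx = 10; exit at TV3 leaves 2, a 5-fold rise.
- TV1–TV4: 5 falls to 2, a 2.5-fold rise.
- TV2–TV5: 5 falls to 0.5, a 10-fold rise. Exit at TV2 leaves one point and no slope.

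**The case against.** A reader might infer that the clause biases the trial towards geko or raises its false-positive rate. The documents do not support that. LHR is a weekly rate, so a shorter window does not bias it while healing stays linear, and the shift is zero if the device does nothing. Only the geko arm is modelled above. SC participants can be removed under the same clause, and with no rates by arm no net between-arm shift can be computed.

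A reader might also infer that under-using the device leads to exit. That is not shown. The diary (Appendix 6) provides for days of non-use, section 11.2.1 lists interrupted and discontinued treatment as separate outcomes, and section 4.6 has missed visits made up. Section 5.2 itself names stopping treatment and leaving the study separately, so a site may already stop the device and keep the participant. The model in step 3 is therefore a bound, not a forecast. If non-compliance means not attending, no rule recovers the images.

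Other points stand in part:
- The 20% comes from the superseded 126-subject plan and covers every cause of discontinuation.
- TV5 assessments preserve an exit image, so only later images are lost.
- Section 10.11 counts withdrawn participants as treatment failures, which bears on healing incidence. It gives the same label to everyone unhealed and assigns no LHR value.
- How to compute LHR from fewer than four measurements is a separate missing-data question, which also arises with early healing.

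None of this supplies a rule that keeps a participant judged significantly non-compliant under observation.

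**Conclusion.** The point holds as a gap in outcome collection. The text allows exit from the study for non-compliance or deviations, and that exit truncates the ITT primary LHR. The loss is of images and of the as-allocated comparison for the few people concerned, in a trial of 60. The shift in the geko mean is 0 to 0.035 mm/week over the whole arm with a one-visit lag and up to 20% affected. It reaches 0.093 only if all of that 20% leave the moment use stops after week 1. The part still correctable is about 0.014 mm/week at most with a one-visit lag, if 60% of the arm has finished. These figures rest on assumed shares, lags and a full 0.58 gain that ends with device use. The change is worth making because it is cheap and a later SAP cannot replace it; it is not a fatal defect. Confidence is medium, because the documents do not show how often the clause is used.

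**What to change.** In sections 5.2 and 13.4, state that after randomisation non-compliance or a protocol deviation may lead to stopping the device or to exclusion from the per-protocol set, but not by itself to leaving the study. Participants in both arms who are willing to attend continue the scheduled weekly visits, images and VAS to TV5, and then receive the follow-up calls. For them, EOT is the first of TV5, first closure, withdrawal of consent, loss to follow-up or medically necessary withdrawal. Analyse them in the allocated arm.

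Leave unchanged the investigator's right to discontinue for medical need and the revascularisation, non-compressible-ulcer and merging-ulcer reasons. Those reasons also shorten the window, and this change does not reach them.

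Cost: an amendment with ethics approval before use (section 13.3), at sites in several countries. It reaches only later participants who still attend, about 2 in the geko arm under step 4 at 20% affected. It adds no visits beyond those already scheduled. The estimate may be slightly less favourable. At n = 25, a fall of 0.014 mm/week takes paired-t power from about 82% to 80%; the whole-arm bound of 0.035 would take it to 77%.
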